A skin sample was taken following the standard procedure described for the diagnosis of mycosis (5). The epithelial surface was disinfected with 70° alcohol and a sample was collected from the affected area by scalpel scraping. Subsequently, the sample was analyzed using two different procedures. The 30% KOH test (35.3g/100ml distilled water) (Labbox, Barcelona, Spain) followed by conventional light microscopy observation to identify the infective fungal agent, and microbiological culture on Sabouraud dextrose agar with chloramphenicol and cycloheximide (Condalab, Torrejón de Ardoz, Madrid), at a constant temperature (between 25°C and 28°C) for 2 to 4 weeks, in order to inhibit molds and bacteria and observe the growth of the infective fungal agent. Participants with infection were considered to be those who had positive results in both tests, excluding cases in which only one test was positive.

- Bacteriological culture

A skin sample was taken following the standardized procedure for microbiological analysis (6). The skin was disinfected with 70° alcohol and a sample was taken by smear with a sterile swab from the affected surface. Again, the analysis was carried out using two distinct and independent procedures. A Gram stain was performed to identify bacteria and the sample was inoculated with Sabouraud dextrose broth (SDA) (Merck, Germany), at a constant temperature (between 27°C and 31°C) for 1 to 3 days. Participants with infection were considered to be those who had positive results in both tests, excluding cases in which only one test was positive.

Variables and statistical analysis

The following variables were analyzed: sociodemographic (sex and age), anthropometric (weight, height, and BMI), hygiene-related habits (frequency of foot washing, use of flip-flops in showers/pools, type of footwear and socks and frequency of sock change), presence or absence and type of infection, degree of hydration and concentration of EC group T0 (0%), group T1 (1%) and group T2 (0.5%). Of these variables, age, weight, height, BMI, and hydration were considered quantitative compared to the rest that were analyzed as qualitative.

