Statistical analysis was performed using the statistical analysis program IBM-SPSS Statistics for Windows version 25 (IBM Corp. Armonk, NY, USA). Some figures have been obtained using the Python programming language, using the Seaborn library (Waskom, M. L., (2021). Seaborn: statistical data visualization. *Journal of Open-Source Software*, 6(60), 3021, <https://doi.org/10.21105/joss.03021>).

Normality was assessed using the Shapiro-Wilk test. To evaluate the influence of different variables on infection remission, a Cox regression model was used, and survival curves of significant factors were plotted. To compare the efficacy of different EC concentrations, survival curves were compared using the Log-rank test. The Mann-Whitney U test was used to assess hydration averages according to sex. To check if there were improvements in hydration due to the use of the cream with different concentrations of EC (T1 and T2) compared to the control group (T0), hydration levels were compared using Kruskal-Wallis tests, using the Mann-Whitney U test with correction of p-values by the Bonferroni method for multiple comparisons.

In all statistical tests, significance was considered when p-value<0.05 and high significance when p-value<0.01.

2. Results

Analysis of the Elemental Composition of Commercial S. S.

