The determination of the specific composition of the 3 types of EO made it possible to quantify the exact concentration of the different components of each of the EO, choosing the EO with the highest concentration of components with antimicrobial activity and the lowest concentration of components susceptible to interaction with other drugs or to produce allergies in the participant, such as terpinolene, alpha-terpinene and sabinene and the aged components of EO(7-10). Specifically, the main component in the 3 EO samples was terpinen-4-ol, with a concentration between 28.47% and 29.15%, followed by gamma-terpinene and alpha-terpinene (Table 2). These three components accounted for approximately 65% of the total EO in the 3 samples analyzed. On the other hand, alpha-terpineol and eucalyptol were found to be the fourth and fifth most concentrated components, with percentages between 3.85%-5.85% and 4.12%-5.81%, respectively. These two, along with m-cymene, alpha-pinene, and terpinolene, made up about 24% of the total EO. The rest of the EO was made up of up to 22 different compounds with minority percentages, considered together as traces. For all the above results, the EO of *M. alternifolia* of the brand Esencias Lozano® was used, since it was the EO that presented the highest percentage of the components of terpinen-4-ol, eucalyptol and alpha-terpineol, whose antimicrobial activity has been described in the bibliography(7,11-14).

Table 2. Percentages of the different components according to the EO studied in the CG-MS.

Components	Trademarks of EO		
	Naissance®	Marnys®	Esencias Lozano®
Terpinen-4-ol	28.47%	29.10%	29.15%
Gamma-terpinene	21.92%	20.42%	22.86%
Alpha-Terpinene	13.10%	11.23%	13.58%
Alpha-terpineol	3.85%	4.03%	5.85%
Eucalyptol	4.12%	4.82%	5.81%
M-cymene	3.40%	5.28%	4.96%
Alpha-pinene	3.18%	3.15%	5.12%
Terpinolene	4.65%	4.26%	3.72%
Traces	17.31%	17.71%	8.95%
Total	100%	100%	100%

®: trademark; %: percentage of the component in the sample.

Test results for microbiological diagnostics

After reading the tests performed for microbiological diagnosis, it was determined that, of the 49 total participants, 32 (65.3%) were positive for skin infections. Of these 32 participants, 4 (12.5%) had fungal infection, 19 (59.4%) showed bacterial infection, and 9 (28.1%) had mixed fungal and bacterial infections simultaneously.

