	East.	Err. East	IC 95%		East.	Err. East	IC 95%	
			Lim. Inf.	Lim. Sup.			Lim. Inf.	Lim. Sup.
Treatment 1%	11.61	2.68	6.36	16.86	-	-	-	-
Treatment 0.5%	14.00	4.04	6.09	21.91	-	-	-	-

Est: statistical survival test; Err. Est: statistician error; CI, confidence interval; Lim. Inf: lower bound; Lim. Sup: upper limit; "-": data not available.

Similarly, to evaluate whether the EO-enriched cream was effective against bacterial infections, the cumulative survival curves for both treatments were plotted (Figure 5). In this case, the treatment curve at 0.5% concentration showed better results than the 1% treatment curve.

[figure not shown]

Figure 5. Cumulative survival curves as a function of the two treatments for bacterial infections.

Thus, the mean time to achieve remission in the T1 group (1%) was 49.35 days, compared to 44.82 days in the T2 group (0.5%) (Table 5). This indicated that the treatment of the T2 group was better, since the infection remitted 5 days earlier on average, although when comparing both treatments using the Long-rank test, no statistically significant differences were found (p -value=0.130). Median survival was 60.00 days for treatment at 0.5%, so half of the participants in the T2 group achieved remission at the end of the study. This value could not be computed for the 1% treatment, indicating that less than half of the subjects in this group experienced resolution of the infection at the end of the trial (Table 5).

Table 5. Mean and mediansurvival time (in days) of remission of bacterial infection for the two EC concentrations.

Group	Media				Median			
	East.	Err. east.	IC 95%		East.	Err. east.	IC 95%	
			Lim. Inf.	Lim. Sup.			Lim. Inf.	Lim. Sup.
Treatment 1%	49.35	2.38	44.68	54.01	-	-	-	-
Treatment 0.5%	44.82	4.38	36.2	53.40	60.0	6.37	47.51	72.49

Est: statistical survival test; Err. Est: statistician error; CI, confidence interval; Lim. Inf: lower bound; Lim. Sup: upper limit; "-": data not available.

Relationship between infections and the rest of the variables analyzed

In relation to hygiene habits, it was found that most of the participants washed their feet daily, used flip-flops in swimming pools or showers, wore breathable footwear and cotton socks, and changed their socks daily (Table 6), although it is true that these habits did not show a statistically significant relationship with respect to the presence or absence of skin infections ($p\text{-value} \geq 0.103$) (Table 7).

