Table 6. Contingency table between hygiene habits and skin infections.

Category	Fungal infection		Total	Bacterial infection		Total
	No	Yes		No	Yes	
Frequency of foot washing						
1 time every 2 days	2 (4.88%)	-	2 (4.08%)	2 (6.90%)	-	2 (4.08%)
Daily	33 (80.49%)	8 (100.00%)	41 (83.67%)	23 (79.31%)	18 (90.00%)	41 (83.67%)
2 times a day	6 (14.63%)	-	6 (12.24%)	4 (13.79%)	2 (10.00%)	6 (12.24%)
Total	41 (83.67%)	8 (16.33%)	49	29 (59.18%)	20 (40.82%)	49
Flip flops in the shower						
No	7 (17.07%)	2 (25.00%)	9 (18.37%)	8 (27.59%)	1 (5.00%)	9 (18.37%)
Yes	34 (82.93%)	6 (75.00%)	40 (81.63%)	21 (72.41%)	19 (95.00%)	40 (81.63%)
Total	41 (83.67%)	8 (16.33%)	49	29 (59.18%)	20 (40.82%)	49
Type of footwear						
Non-breathable	18 (43.90%)	4 (50.00%)	22 (44.90%)	12 (41.38%)	10 (50.00%)	22 (44.90%)
Breathable	23 (56.10%)	4 (50.00%)	27 (55.10%)	17 (58.62%)	10 (50.00%)	27 (55.10%)
Total	41 (83.67%)	8 (16.33%)	49	29 (59.18%)	20 (40.82%)	49
Sock Type						
Cotton	21 (51.22%)	6 (75.00%)	27 (55.10%)	17 (58.62%)	10 (50.00%)	27 (55.10%)
Polyester	10 (24.39%)	-	10 (20.41%)	6 (20.69%)	4 (20.00%)	10 (20.41%)
I don't know	10 (24.39%)	2 (25.00%)	12 (24.49%)	6 (20.69%)	6 (30.00%)	12 (24.49%)
Total	41 (83.67%)	8 (16.33%)	49	29 (59.18%)	20 (40.82%)	49
Daily sock change						
1 time every 2 days	5 (12.20%)	-	5 (10.20%)	1 (3.45%)	4 (20.00%)	5 (10.20%)
Daily	32 (78.05%)	8 (100.00%)	40 (81.63%)	26 (89.66%)	14 (70.00%)	40 (81.63%)
2 times a day	4 (9.76%)	-	4 (8.16%)	2 (6.90%)	2 (10.00%)	4 (8.16%)
Total	41 (83.67%)	8 (16.33%)	49	29 (59.18%)	20 (40.82%)	49

"-": data not available, %: percentage.

Table 7. Relationship between hygiene habits and skin infections.

Variables	Fungal infection		Bacterial infection	
	χ^2	p-value	χ^2	p-value
Frequency of foot washing	1.87	0.393	1.68	0.432
Flip flops in the shower	0.00	0.976	2.66	0.103
Type of footwear	0.00	1.000	0.09	0.761
Sock Type	2.64	0.267	0.58	0.748
Daily sock change	2.15	0.542	4.08	0.252

χ^2 : Chi-Square

On the other hand, the possible relationship between anthropometric and sociodemographic variables and treatment efficacy for fungal infections was examined, where no statistically significant association was observed ($p\text{-values} \geq 0.145$) (Table 8). Therefore, for this sample, anthropometric and sociodemographic variables did not seem to be critical factors in the efficacy of treatment for fungal infections of the foot.

Table 8. Cox model for different anthropometric and sociodemographic variables and fungal infection.

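### The hygiene conclusion is worded for any skin infection, but Tables 6 and 7 test only fungal and bacterial infection separately, each with a reference group that includes people who have the other type

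*Combined protocol and SAP*

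**What the plan says.** The *Variables and statistical analysis* section lists "presence or absence and type of infection" among the analysed variables, so both questions, infected or not and which type, are in scope. It sets the threshold for all tests: "In all statistical tests, significance was considered when p-value<0.05 and high significance when p-value<0.01".

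Under *Test results for microbiological diagnostics*, "of the 49 total participants, 32 (65.3%) were positive for skin infections". Of these, "4 (12.5%) had fungal infection, 19 (59.4%) showed bacterial infection, and 9 (28.1%) had mixed fungal and bacterial infections simultaneously".

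Under *Relationship between infections and the rest of the variables analyzed*, the conclusion is that "these habits did not show a statistically significant relationship with respect to the presence or absence of skin infections" (p at least 0.103), with reference to Table 7. Tables 6 and 7 cross five habits with fungal infection (8 yes, 41 no) and with bacterial infection (20 yes, 29 no). Neither table has a column for any infection.

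**The concern.** The sentence answers a question that the tables do not ask. In each table the No column is not a group of uninfected people: it also holds those infected only by the other organism type. If a habit raises the risk of both types, it is over-represented in the Yes column and in part of the No column, so the contrast shrinks. At stake is a null statement about hygiene and foot infection in general, which a reader would take as tested in 49 people.

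**Working it through.** **Reproducing the reported bound.** The smallest p-value is flip-flops against bacterial infection. Table 6 gives non-users 8 no, 1 yes and users 21 no, 19 yes. With the Yates correction:

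χ² = 49 × (|8×19 − 1×21| − 24.5)² / (9×40×29×20) = 49 × 106.5² / 208,800 = 2.66, p = 0.103, as printed.

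Without the correction, χ² = 49 × 131² / 208,800 = 4.03, p = 0.045; Fisher's exact p = 0.064. Reading the dash cells of Table 6 as zero (the rows add up that way), eight of the ten cells of Table 7 reproduce. The two sock-change cells do not: the fungal χ² of 2.15 matches, but p = 0.542 needs 3 degrees of freedom where the printed three-row table has 2 (p = 0.341); the bacterial cell recomputes to 3.88, p = 0.144, against 4.08 and 0.252.

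**Who is in the reference groups, by the diagnoses.**
- Any fungal: 4 + 9 = 13. No fungal: 49 − 13 = 36, of whom 19 have bacteria: 19/36 = 53%.
- Any bacterial: 19 + 9 = 28. No bacterial: 49 − 28 = 21, of whom 4 have fungus: 4/21 = 19%.
- Uninfected: 49 − 32 = 17.

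**Who is in them, by Table 6.** At most 8 of the 20 bacterial positives can be among the 8 fungal positives, so the fungal No group of 41 holds at least 12 bacterial positives (12 to 20). The bacterial No group of 29 holds 0 to 8 fungal positives. Even with no overlap, 8 + 20 = 28, below 32, so at least 4 infected participants are No in both columns. If 32 are infected, the No columns contain 32 − 8 = 24 of 41 (59%) and 32 − 20 = 12 of 29 (41%).

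**Size of the dilution (illustrative).** Assumptions: the diagnosis counts; a two-category habit; the same odds ratio (OR) of 4 for every infection type; habit prevalence 30% in the uninfected.
- Odds 0.30/0.70 = 0.429; × 4 = 1.714; prevalence in the infected 0.632.
- Fungal reference: (17×0.30 + 19×0.632)/36 = 0.475, odds 0.905; apparent OR 1.714/0.905 = 1.89.
- Bacterial reference: (17×0.30 + 4×0.632)/21 = 0.363, odds 0.570; apparent OR 1.714/0.570 = 3.01.

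Over prevalences of 20% to 50% the apparent ORs are 1.8 to 2.1 and 2.9 to 3.2.

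**Power at OR 4**, by enumerating the binomial outcomes at prevalences of 20%, 30% and 50%, uncorrected Pearson test at 0.05:

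| Habit acts on | Any, 32 v 17 | Fungal, 13 v 36 | Bacterial, 28 v 21 |
|---|---|---|---|
| Both types alike | 58–63% | 13–16% | 42–48% |
| Fungal only | 13–15% | 49–58% | – |
| Bacterial only | 46–52% | – | 60–66% |

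With the Yates correction the first row becomes 40–48%, 6–9% and 28–35%.

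**Would the conclusion change?** The any-infection table needs the fungal-by-bacterial overlap within each habit, which is not printed. Taking every table compatible with the Table 6 margins and 32 infected, with the test the document used, p ranges over:
- foot washing: 0.022 to 0.897
- flip-flops: 0.009 to 1.000
- footwear: below 0.001 to 1.000
- sock type: below 0.001 to 0.925
- sock change: 0.053 to 0.677

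If only the Table 6 positives count as infected (20 to 28 people), no compatible table falls below 0.05 with that test.

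**The case against.** The strongest reply is that analysis by type is a legitimate choice, is within the listed variables, and is labelled plainly in the column headings. For a habit linked to one type the existing rows are the more powerful test, as the table shows. Pooling could also cancel effects that run in opposite directions, and the flip-flop rows do: fungal infection in 2/9 non-users v 6/40 users (22% v 15%), bacterial in 1/9 v 19/40 (11% v 47.5%). The counts are small, but nothing in the documents supports a common odds ratio. The analysis is also secondary and does not feed the efficacy or hydration comparisons. All of this stands. It rules out replacing the type-specific rows, but does not supply the missing any-infection test.

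A reader might infer that the design of Table 7 dilutes every association. It does not; dilution requires a habit that acts on both types in the same direction. A reader might also infer that a real hygiene effect has been missed, pointing to the uncorrected p of 0.045 for flip-flops. The documents do not support that either: Fisher's test gives 0.064, this is one of ten tests, and the any-infection p-values are undetermined.

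**Conclusion.** The concern holds as a gap between the conclusion and the analysis. No comparison of 32 infected with 17 uninfected is reported, and both reference groups contain infected people by the diagnoses, so a statement about any infection is unsupported. What Table 7 reports is the narrower result: no significant association with fungal infection, or with bacterial infection, each taken separately. With so few cases even that is not evidence of no relationship.

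The dilution is conditional. It is heavy in the fungal table and modest in the bacterial table if a habit affects both types alike, and absent if it affects one type. The odds ratios and power figures rest on an assumed common odds ratio, a two-category habit (three of the five have three categories) and the diagnosis counts rather than the Table 6 counts. The main power figures also use an uncorrected test, whereas the 2×2 rows of Table 7 used the Yates correction. They show direction and rough size only.

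**What to change.** 1. Reconcile Table 6 (8 fungal, 20 bacterial) with the diagnoses (13 and 28, 32 infected in all), and correct the sock-change cells of Table 7. Any re-tabulation depends on this.
2. Beside the existing type-specific rows, add for each habit an exact test of any infection (32) against none (17), with an estimate and confidence interval. Each type against the 17 uninfected may be added as a sensitivity row.
3. Until then, limit the sentence to no significant association with fungal or with bacterial infection taken separately.

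The cost is re-tabulation of data already collected, or an edit to one sentence. The downsides are five more tests in a small sample and an any-infection test that is weaker than the existing rows for a habit linked to one type. The sensitivity row has a similar price: at OR 4, fungal cases against the 17 uninfected have 39–45% power, which beats 13–16% if the habit acts on both types but falls short of 49–58% if it acts on fungi only. For these reasons the new rows should supplement the existing ones.

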Scans and measurements were performed in a temperature-controlled room (20-24°C) and participants aired their bare feet for 10 minutes before starting the procedures, to normalize the temperature. In the first session they were weighed and measured (SECA 701, Vogel & Halke Hamburg, Germany), calculating the BMI(2). After normalizing the temperature, the physical examination was carried out, samples were taken, and data were obtained.

The Corneometer CM 825® (Electronic Courage-Khazaka, Cologne, Germany) with a measuring surface of 49 mm, a frequency of 0.9–1.2 MHz and an accuracy of $\pm 3\%$, was used to assess the superficial hydration of the skin (3). Five reference points were measured, both at the dorsal level and at the plantar level (Figure 2), obtaining three measurements from each point to later calculate the average hydration of each location analyzed.

[figure not shown]

Figure 2. Location of the 5 reference points on the feet for assessment of superficial hydration. (A) Dorsum of the foot: (1) dorso-distal point, above the central metatarsal heads. (B) Sole of the foot: (2) interdigital-plantar point, between 3rd and 4th digital space, (3) central point of the internal arch, (4) central point of the external arch, and (5) central point of the calcaneus.

Regarding the diagnosis of possible infections present in the feet, the following tests were performed:

- Wood's Light Examination

The feet of the participants were examined with a Wood L1004® lamp (Weelco, Barcelona, Spain) at maximum power (41) and at a distance of 10-15 cm from the surface to be examined. Long-wave ultraviolet radiation allows visual observation of the fluorescence emitted by *Pseudomonas aeruginosa*, *Microsporum audouinii*, *Microsporum canis*, *C. minutissimum*, *T. schoenleinii*,(4) among

others, whose color varies depending on the pathogen. The areas that fluoresced were recorded along with the color of the fluorescence in each review conducted from the beginning of the study to the day of its completion.

- Potassium hydroxide (KOH) test and mycological culture

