Of the participants who developed skin infections, 23 were women and 9 were men. The prevalence of skin infections by sex is shown in Table 3.

Table 3. Prevalence of infections as a function of sex.

Sex	Infections			Total
	Fungal	Bacterial	Mixed	
Women	3 (9.3%)	13 (40.6%)	7 (21.8%)	23 (71.7%)
Men	1 (3.1%)	6 (18.8%)	2 (6.4%)	9 (28.3%)
Total	4 (12.4%)	19 (59.4%)	9 (28.2%)	32 (100%)

%: Percentage.

The colorations observed with Wood's light in the interdigital spaces were coral red and opaque blue (Figure 3). The coral-red coloration corresponds to a superficial bacterial infection of the skin caused by *C. minutissimum*, known as erythrasma, and the dull blue coloration corresponds to a fungal infection caused by the dermatophyte *Trichophyton schoenleinii*.

[figure not shown]

Figure 3. Fluorescence of different color emitted by pathogens under Wood's light in interdigital spaces of the feet. (A and B) erythrasma with coral-red coloration (*) and (B) suspected *Trichophyton schoenleinii* with bluish coloration (↑).

Mycological cultures were used to determine the causative agents of fungal infections. The dermatophytes and yeasts that were identified were: *Trichophyton schoenleinii*, *Trichophyton verrucosum*, *Trichophyton tonsurans* and *Candida albicans*. On the other hand, the following bacteria were identified in bacterial cultures: *Corinebacterium minutissimum*, *staphylococcus haemolyticus*, *staphylococcus epidermidis*, *staphylococcus lugdunensis*, *micrococcus luteus* and *micrococcus sp.*

Efficacy of treatments

To test whether the EC-enriched cream was effective against fungal infections, the cumulative survival curves of the two treatments, T1 and T2, were plotted (Figure 4). 100% of fungal infections resolved within 30 days with both treatments, although the EC curve at 1% was higher than 0.5%.

[figure not shown]

Figure 4. Cumulative survival curves as a function of the two treatments for fungal infections.

In fact, the mean time to achieve remission in the T1 group (1%) was 11.61 days, compared to 14.00 days in the T2 group (Table 4). However, according to the Log-rank test, the differences between the two groups were not statistically significant (p -value=0.611). Therefore, both concentrations have similar efficacy in terms of the time required to achieve remission of infection.

Table 4. Mean and median survival time (in days) of remission of fungal infection for the two EC concentrations.

Group	Media				Median			

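### The fungal time-to-remission results (Table 4, its log-rank test, Table 8) cannot come only from the documented fungal infections with remission dated at follow-up visits, and the body-size rows are redundant

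*Combined protocol and SAP*

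**What the plan says.** The statistical section plans the model in one sentence: "To evaluate the influence of different variables on infection remission, a Cox regression model was used". It does not name the covariates, their coding, the analysis set or the unit of analysis. The examination section records weight and height, "calculating the BMI" from them.

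The microbiology results report that "4 (12.5%) had fungal infection, 19 (59.4%) showed bacterial infection, and 9 (28.1%) had mixed fungal and bacterial infections simultaneously". The control group had no infections, so 4 + 9 = 13 treated participants had a fungal infection. Table 6 shows 8.

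The efficacy section states that "100% of fungal infections resolved within 30 days with both treatments", and that "the mean time to achieve remission in the T1 group (1%) was 11.61 days, compared to 14.00 days in the T2 group". Table 4 gives no median for either arm. The reported log-rank p is 0.611, from which the text concludes that "both concentrations have similar efficacy in terms of the time required to achieve remission of infection".

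Tables 8 and 9 list stature, weight, BMI, age and sex. No table gives the number of records or events behind Table 4, 8 or 9. The Table 8 text concludes that "for this sample, anthropometric and sociodemographic variables did not seem to be critical factors in the efficacy of treatment for fungal infections".

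**The concern.** Reviews took place on days 15, 30, 45 and 60, and follow-up cultures only on days 30 and 60. A mean time to remission below 15 days therefore needs records whose remission is dated before anyone was reviewed. If such records belong to people without a fungal infection at baseline, the log-rank test and the Table 8 hazard ratios partly describe who was uninfected at the start, not who responded to treatment.

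Separately, a model holding stature, weight and a function of both cannot estimate any one of them usefully. Its non-significant rows say nothing about body size. Two firm conclusions rest on these analyses: similar efficacy of the two concentrations, and no important role for patient characteristics.

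**Working it through.** **Inputs.** Table 4: T1 (1%) mean 11.61, SE 2.68, CI 6.36–16.86; T2 (0.5%) mean 14.00, SE 4.04, CI 6.09–21.91. Tables 8 and 9: 95% limits. Table 1: SD of height 0.085 m, weight 12.705 kg, BMI 3.626. Visit and culture days and arm sizes (25 and 12): randomization and design section.

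**1. The printed figures agree with each other.** Mean ± 1.96 × SE gives 6.36–16.86 for T1 and 6.08–21.92 for T2, as printed up to rounding. A Wald comparison gives z = (14.00 − 11.61)/√(2.68² + 4.04²) = 0.493, p = 0.62, close to the log-rank 0.611.

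**2. Means against visit days.** If a share q is dated day 0 and the rest day t, the mean is (1 − q)t, so q = 1 − mean/t.

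| | rest at day 15 (minimum q) | rest at day 30 |
|---|---|---|
| T1 | 1 − 11.61/15 = 23% | 1 − 11.61/30 = 61% |
| T2 | 1 − 14.00/15 = 7% | 1 − 14.00/30 = 53% |

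Counting feet instead of participants does not change this.

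**3. Medians.** If all infections resolved by day 30, the curve reaches zero and must cross one half, so a median exists. For bacterial infection (Table 5) the document reads a missing median as fewer than half resolved. That reading of Table 4 would contradict full resolution.

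**4. Events behind Table 8.** SE = ln(upper/lower)/3.92. For sex, ln(1.35/0.20)/3.92 = 0.487. For a 0/1 covariate each event adds at most 1/4 to the Cox information, and further covariates only reduce precision, so events ≥ 4/SE² = 16.9. With the widest limits that round to those printed (0.195–1.355) the bound is 16.4, so at least 17 whole events. With 13 events the SE cannot be below 2/√13 = 0.555; with 8, not below 0.707.

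**5. Redundant terms.** Implied SEs for stature, weight and BMI:

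- Table 8: 0.147, 0.166, 0.464, ratio 1 : 1.13 : 3.15.
- Table 9: 0.161, 0.189, 0.525, ratio 1 : 1.17 : 3.27.
- Expected for joint entry: about 1 : 1.2 : 3.2.
- Expected for separate models: about 1 : 0.67 : 2.1–2.5.

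The expected ratios use the Table 1 SDs, stature in cm and a height–weight correlation of 0.50–0.70. The last two are assumptions; a correlation of about 0.63 returns the printed BMI SD. The printed ratios match joint entry. On the same assumptions, with or without sex in the model, variance inflation is roughly 40–65 (height), 125–215 (weight) and 75–140 (BMI), so SEs are about 6–8, 11–15 and 9–12 times wider.

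**6. A data pattern that reproduces Table 4.** Take 31 T1 records with 19 at day 0 and 15 T2 records with 8 at day 0, and put all other remissions at day 30. The means are 30 × 12/31 = 11.61 and 30 × 7/15 = 14.00. The Greenwood SEs are 2.624 and 3.864. Multiplying the variances by m/(m − 1), with m = 25 and 12 events, gives 2.679 and 4.036, and the printed intervals follow. This leaves 6 T1 and 3 T2 records censored before day 30 (m = 26, with 5 censored, also fits T1). At day 0 the log-rank has O − E = 19 − 27 × 31/46 = 0.804 and V = 2.505, so χ² = 0.258 and p = 0.611. Day 30 adds nothing, because every record still at risk remits then.

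**The case against.** The strongest objection is to step 6. A reader might infer from the match to p = 0.611 that uninfected participants are proven to have been entered as day-0 remissions. The documents do not support that:

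- The pattern needs 46 records against 37 treated participants.
- It needs early censoring that nothing in the document describes.
- It needs a variance factor that the document does not state.
- Its 12 non-day-0 records in T1 and 7 in T2 cannot be identified with participants.
- The p match adds little, because step 1 shows that the Table 4 means and SEs already imply p of about 0.6.

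This objection stands in full, so step 6 is only a possible explanation. Steps 2 to 5 do not use it.

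Remission might also have been dated at interval midpoints, which would allow times before day 15. The document describes no such rule, and a limited search (up to 16 records on three-time grids and 31 on two-time grids) found no match. It would not resolve the event count in step 4.

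Counting feet could raise the number of events above 13, but the document never says feet were counted, and this leaves step 2 untouched.

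Event counts inferred from the other Table 8 rows depend on unstated scales. The age row gives an impossible count if age is in years. Only the sex bound is used here.

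Finally, the body-size rows are secondary and the Table 8 conclusion is hedged. That is fair, and the weightier consequence is for the efficacy statement. Nor should a reader infer that the redundancy spoils the sex and age rows: they are much less affected, and their weakness is imprecision and the unknown analysis set.

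**Conclusion.** The point holds on the printed figures. Three findings carry it:

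- The Table 4 means are impossible for remission dated at reviews from day 15 on. At least 23% (T1) and 7% (T2) of records must be dated day 0, and 61% and 53% if the others remit at day 30.
- With 0/1 coding, Table 8 needs at least 17 events, against 13 or 8 documented fungal infections.
- The stature, weight and BMI rows of Tables 8 and 9 are uninformative, given joint entry. Joint entry is inferred from the SE ratios and assumes stature in cm.

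Non-significance with intervals such as 0.39–2.40 for BMI and 0.20–1.35 for sex cannot support a conclusion of no important influence. Nor does p = 0.611, in at most 13 documented infections, show similar efficacy. This is not evidence that the concentrations differ or that the cream fails; the analysis cannot tell. Which records were dated day 0, and why, can be settled only from the analysis file.

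**What to change.** 1. Check the analysis file. State the analysis set, unit (participant or foot), number analysed, number of events, rule for dating remission and covariate coding. Reconcile 13 fungal infections with 8. Restrict Table 4, Table 8 and the fungal log-rank test to participants with fungal infection at baseline, with no day-0 remissions.
2. If all remaining fungal remissions fall at one visit, there is no time-to-event information left. Drop the log-rank test, mean times and fungal Cox model, and report the proportion resolved by arm with exact intervals. When all n resolve, the lower limit is 0.025^(1/n): overall, 13/13 would give 75–100% and 8/8 would give 63–100%; by arm they would be wider. If remissions fall at several visits, use very few covariates.
3. In the bacterial model use BMI alone, or height and weight without BMI, in participants with bacterial infection at baseline.
4. Whatever the check finds, replace both the similar-efficacy statement and the statement on critical factors by one saying that the data are too imprecise to show or exclude a difference. Confirming the analysis set would not establish similarity.
5. Correct the lower bound of 0.145 quoted for the Table 8 p-values; the smallest there is 0.181.

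The cost is a file check, a rerun and text edits. Separate height and weight estimates are lost if BMI is used, and possibly the whole fungal time-to-event comparison.
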